7.2. Pharmacokinetic Analyses

7.2.1. Overview of Planned Radio-Pharmacokinetic Analyses

The radio-PK analyses will be based on the PK population, unless otherwise specified. Influx rate constant (K_i) will be used as the imaging metric for ^{11}C -MET dynamic scan.

[Table 4](#) provides an overview of the planned Radio-PK analyses, with further details of data displays being presented in [Appendix 11](#): List of Data Displays.

Table 4 Overview of Planned Radio-Pharmacokinetic Analyses.

Endpoint / Parameter/ Display Type	Untransformed ¹				
	Stats Analysis		Summary	Individual	
	T	F	T	F	L
Radioactivity concentrations (whole blood and plasma)					
static ¹⁸ F-FDG PET/CT					Yes
¹¹ C-MET PET/CT			Yes	Yes ^{2,3}	Yes
Radiopharmacokinetic parameters (¹¹C-MET)					
Influx rate constant (K _i)	Yes ³	Yes ³	Yes		Yes
Administration Volume					
Tracer and contrast					Yes
Meal Ingested					
Totality of Meal ingested					Yes

NOTES:

- T = Table, F = Figure, L = Listings
- Stats Analysis = Represents TFL related to any formal statistical analyses (i.e. modelling) conducted.
- Summary = Represents TFL related to any summaries (i.e. descriptive statistics) of the observed raw data.
- Individual = Represents FL related to any displays of individual subject observed raw data.
- [1]: Log_e transform if necessary
- [2]: By subject group for ¹¹C-MET
- [3]: Correlation between radioPK parameter (K_i) vs ¹¹C-MET PET/CT SUV_{peak/mean/max} by the side of the gland with most/least uptake in and ROI.

7.2.2. Radiopharmacokinetic Parameters**7.2.2.1. Deriving Radiopharmacokinetic Parameters**

Derivation of the influx rate constant (K_i) is described in the PET data acquisition and analysis protocol and the derived endpoint will be received from Imanova.

7.2.2.2. Statistical Analysis of Radiopharmacokinetic Parameters

Tracer concentrations in whole blood and plasma will be summarized and listed by subject groups for static ¹⁸F-FDG and ¹¹C-MET and Dynamic ¹¹C-MET. Individual, concentration-time curves will be plotted. The radio-pharmacokinetic parameter Influx Rate Constant (K_i) for ¹¹C-MET PET/CT will be summarized and listed by subject groups.

¹¹C-MET Influx rate constant (K_i) from dynamic ¹¹C-MET PET/CT scan will be graphically compared to ¹¹C-MET static scan SUV_{peak/mean/max} or parameters derived by normalization with blood or other references, in the salivary gland region using a scatter plot by subject group. In addition to this, the correlation will be calculated and summarised between these parameters to compare static and dynamic imaging metrics.

8. SAFETY ANALYSES

8.1. Overview of Planned Adverse Events Analyses

The Safety analyses will be based on the Safety population, unless otherwise specified. [Table 5](#) provides an overview of the planned analyses, with further details of data displays being presented in [Appendix 11](#): List of Data Displays.

Table 5 Overview of Planned Adverse Event Analyses

Endpoint / Parameter/ Display Type	Absolute ¹	
	Summary	Individual
	Table	Listing
Adverse Events (AEs)		
All AEs by SOC	Yes	Yes
Common AEs by Overall Frequency ²	Yes	
Subjects & No. of Occurrences of Common Non-Serious AEs by SOC and PT ²	Yes	
Subject Numbers for Individual AEs		Yes
Relationship Between AE SOCs, PT & Verbatim Text		Yes
Serious and Other Significant AEs		
Reasons for Considering as a Serious AE		Yes
AEs Leading to Withdrawal from Study by Overall Frequency	Yes	Yes
Subjects and Number of Occurrences of Serious and Fatal Serious AEs	Yes	

NOTES:

- SOC = System Organ Class, PT = Preferred Term.
- Summary = Represents TF related to any summaries (i.e. descriptive statistics) of the observed raw data.
- Individual = Represents FL related to any displays of individual subject observed raw data.
- [1]: All outputs by subject group (HV and pSS)
- [2]: Common defined by ≥ 2 subjects

8.2. Overview of Planned Clinical Laboratory Analyses

The Clinical Laboratory analyses will be based on the “Safety” population, unless otherwise specified.

[Table 6](#) provides an overview of the planned analyses, with further details of data displays being presented in [Appendix 11](#): List of Data Displays.

Table 6 Overview of Planned Clinical Laboratory Analyses

Endpoint / Parameter/ Display Type	Absolute
	Individual
	Listing
Chemistry	
Chemistry	Yes
Hematology	Yes
Urinalysis	Yes

Endpoint / Parameter/ Display Type	Absolute
	Individual
	Listing
Other Screening Tests	Yes
Vital Signs	
Vital Signs for Subjects with Values of Potential Clinical Importance (PCI)	Yes

NOTES:

- Summary = Represents TFL related to any summaries (i.e. descriptive statistics) of the observed raw data.
- Individual = Represents FL related to any displays of individual subject observed raw data.

9. OTHER STATISTICAL ANALYSES

9.1. Exploratory Analyses

9.1.1. Overview of Exploratory Analyses

The exploratory analyses will be based on the Safety population, unless otherwise specified.

Table 7 provides an overview of the planned exploratory analyses, with full details of data displays being presented in Appendix 11: List of Data Displays.

Table 7 Overview of Planned Exploratory Analyses

Endpoint	Untransformed				
	Absolute				
	Summary		Individual		Stats Analysis
	T	F	F	L	T
Salivary gland					
Basal and Stimulated salivary flow	Yes		Yes	Yes	Yes ¹
Histological scores ²	Yes		Yes	Yes	Yes ¹
Lacrimal Gland					
Schirmer's test	Yes		Yes	Yes	Yes ¹
Disease index²					
Disease activity measures ³	Yes			Yes	
ESSDAI and ESSPRI			Yes		Yes ¹
ESSDAI component scores	Yes			Yes	
ESSPRI component scores				Yes	
Multiparametric MRI quantitative parameters⁵					
(median and IQR) IRE, (median and IQR) ME, (mean) Lipid Content, (median and IQR) T1 relaxation, (median and IQR) D* and (mean) gland volume	Yes ⁶	Yes ⁶		Yes ⁶	Yes ^{1,7}
Multiparametric MRI Questionnaire					
Dental History				Yes	
Sjogren's specific biomarkers²					
Laboratory biomarkers of disease activity ⁴	Yes		Yes	Yes	Yes ¹

NOTES:

- T = Table, F = Figure, L = Listing, IQR = Interquartile Range, D* = Psuedo Diffusion
- Summary = Represents TFL related to any summaries (descriptive statistics) of the observed raw data.
- Individual = Represents FL related to any displays of individual subject observed raw data.
- Stats Analysis = Represents TFL related to any formal statistical analyses (i.e. modelling) conducted.
- 1: Summary table for correlation.
- 2: pSS subjects only – more detail below
- 3: These include ESSDAI, ESSPRI, Patient Global Assessment, Physician Global Assessment, Oral dryness

- numerical rating, ocular dryness numerical rating
- 4: This may include metabolomic and proteomic profiles if applicable and also include data from healthy subjects. See Section 11.3.6 for more details.
- 5: If data permits.
- 6: By region of interest (ROI) and group (HV or pSS patient).
- 7: Summary table of comparison between HV and pSS group.

Descriptive statistics (Mean, Median, Standard Deviation, Minimum, Maximum) of absolute values of basal, stimulated salivary flow rate and score from Schirmer's test will be provided. The absolute values will be listed by subject groups.

The histological scores (see Section 11.3.5) and the various disease indices (see Section 11.3.4) – ESSDAI, ESSPRI, Patient and Physician global assessment of disease activity, oral and ocular dryness scales will be descriptively summarized and listed for pSS group only.

Descriptive statistics will be calculated for the exploratory multiparametric MRI quantitative derived parameters listed in Table 7 (as data permits) and presented in tables. All parameters will be listed by group (and ROI, as data permits). Mean (\pm SE bars) will be plotted for each parameter by ROI (if appropriate with panel for each side).

Correlation between ^{18}F -FDG PET/CT (pSS subjects only), ^{11}C -MET PET/CT and MRI parameters (HV and pSS subjects) in the region of the salivary glands (parotid gland) will be explored using scatter plots. Plots will be in panel for each side (most vs least uptake) of the region scanned. The parameters will include, SUV_{peak} for PET/CT and K_{trans} , D and f for multiparametric MRI.

Furthermore, correlation between the imaging parameters mentioned above and

- histological scores (mean and maximum lymphoid organisation score and volume fraction) from the minor salivary gland biopsy
- Salivary flow rate – mean (from baseline and visit 2) stimulated and basal salivary flow rate, and mean difference (stimulated – basal)
- Measures of Disease Activity – ESSDAI and ESSPRI scores
- Lab biomarkers of disease activity – C3 and C4 levels
- Schirmer's test – length of paper wetted by eyes (panel for each side; least and most) and time to completely wet the strip (panel for each side; least and most).

may be explored using scatter plots (panel for each side) and statistical analysis summarised in tables. In addition, SUV_{peak} from the ^{11}C -MET PET/CT will be correlated with the ratio of IgG/IgA using scatter plots and summary tables of the correlation. See below for summary of correlations:

CONFIDENTIAL

203818

Method		11C-MET PET/CT	18F-FDG PET/CT	Multiparametric MRI
	Parameter(s)/Endpoint	SUVpeak	SUVpeak	(median) Ktrans, (median) D, (median) ADC, (median) f, (median) IRE, (median) ME, (mean) Lipid Content, (median) D* (pseudo diffusion), (mean) gland volume
11C-MET PET/CT	SUVpeak		Yes	
18F-FDG PET/CT	SUVpeak	Yes		
Multiparametric MRI	(mean) lipid content	Yes	Yes	Yes ¹
Histological scores	Max lymphocyte focus score	Yes	Yes	Yes
	Mean lymphocyte focus score			
	Max Lymphoid organisation grading			
	Mean Lymphoid organisation grading			
Salivary flow rate	Mean stimulated	Yes	Yes	Yes
	Mean basal			
	Mean difference			
Disease Activity	ESSDAI	Yes	Yes	Yes
	ESSPRI			
Lab biomarkers of disease activity	C3	Yes	Yes	Yes
	C4			
	IgG/IgA			
Schirmer's test	Length wet per minute	Yes	Yes	

[1]: Correlation of lipid content with (median) Ktrans, IRE, ME, D, f, ADC.

If metabolomic and/or proteomic data is available in the study, these may be reported as a separate reporting effort in addition to the final SAC reporting effort. This will not contribute to the CPSR.

9.1.1.1. Comparison of pSS subjects with HV

An exploratory comparison of pSS vs HV may be performed for multiparametric MRI derived exploratory parameters as data permit, to estimate a difference (or ratio if log transformation is needed) with 95% confidence interval obtained from the analysis described in Section 9.1.2.

9.1.2. Planned Imaging Statistical Analyses

Primary Statistical Analyses
Endpoint(s)

 Multiparametric MRI derived parameters; (median and IQR) IRE, (median and IQR) ME, (mean) Lipid Content, (median and IQR) T1 relaxation, (median and IQR) D* (pseudo diffusion) and (mean) gland volume
Model Specification

 Parameters will be statistically analysed using an Analysis of Variance (ANOVA) model. Terms fitted in the ANOVA model will include: Fixed categorical : Subject group (HV or pSS patient)
Model Checking & Diagnostics

 Refer to Appendix 9: Model Checking and Diagnostics for Statistical Analyses : Model Checking and Diagnostics for Statistical Analyses.
Model Results Presentation

 Estimates of Difference (pSS-HV) (or Ratio (pSS/HV) if log_e transformed) and 95% confidence interval for the derived parameters will be presented by ROI¹. Plots of means (difference or ratio) and 95% confidence interval from the model will be generated for each ROI. P-values will not be presented as formal hypothesis is not being tested. The interpretation will be based on point estimates and its precision (95% CI).

NOTES : [1]: When applicable for a given ROI, the analysis will be separated by the side of the ROI having higher parameter values and lower parameter values, and aggregated over both sides.

11. APPENDICES

Section	Appendix
General Considerations for Data Analyses & Data Handling Conventions	
Section 11.1	Appendix 1: Time & Events
Section 11.2	Appendix 2: Data Display Standards & Handling Conventions 
 • Study Treatment & Sub-group Display Descriptors • Baseline Definitions & Derivations • Reporting Process & Standards
Section 11.3	Appendix 3: Derived and Transformed Data 
 • General, Study Population & Safety • Efficacy • Pharmacokinetic • Pharmacodynamic and or Biomarkers
Section 11.4	Appendix 4: Premature Withdrawals & Handling of Missing Data 
 • Premature Withdrawals • Handling of Missing Data
Section 11.5	Appendix 5: Values of Potential Clinical Importance
Section 11.6	Appendix 6: Multicentre Studies
Section 11.7	Appendix 7: Examination of Covariates, Subgroups & Other Strata
Section 11.8	Appendix 8: Multiple Comparisons & Multiplicity
Section 11.9	Appendix 9: Model Checking and Diagnostics for Statistical Analyses
Other RAP Appendices	
Section 11.10	Appendix 10 – Abbreviations & Trade Marks
Section 11.11	Appendix 11: List of Data Displays
Section 11.12	Appendix 12: Example Mock Shells for Data Displays

11.1. Appendix 1 : Time & Events

Time and Events Table – Screening and Baseline Assessments

Procedure	Screening/Baseline Visit	Baseline 2 (FRP only)
		Within 3-8 days prior to Visit 1
Informed consent	X	
Inclusion and exclusion criteria	X	
Demography	X	
Medical history including past and current medical conditions	X	
Full physical exam (including height and weight)	X	
MRI safety questionnaire	X	
Vital signs	X	
Concomitant medication review	X	
ESSDAI	X ¹	
ESSPRI	X ¹	
Oral dryness numerical rating	X ¹	
Ocular dryness numerical rating	X ¹	
Patient global assessment	X ¹	
Physician's global assessment	X ¹	
Basal salivary flow	X	
Stimulated salivary flow (including saliva collection)	X	
Schirmer's test (including tear collection)	X	
Plasma metabolomics/proteomics	X	
Haematology/clinical chemistry [X	
Blood biomarkers for ESSDAI	X ¹	
Autoantibody screen (anti-Sjögren's-syndrome-related antigen A [Anti-SSa], anti Sjögren's syndrome type B [SSb])	X ¹	
FSH/oestradiol (post-menopausal women only)	X	
Serum pregnancy test (FRP)	X ²	
Urine pregnancy test(FRP)		X ²
Urinalysis	X ³	

AE = adverse event; FSH = follicle stimulating hormone; MRI = magnetic resonance imaging; FRP = females of reproductive potential; .ESSDAI = European League Against Rheumatism (EULAR) Sjögren's Syndrome Disease Activity Index; ESSPRI =EULAR Sjögren's Syndrome Patient Reported Index

1. pSS subjects only
2. Females of reproductive potential only.
3. Urine to be sent for urine protein:creatinine ratio if \geq trace proteinuria by dipstick.

Time and Events Table – Study Assessments

Procedure	Visit 1	Visit 2	Follow up
	Within 6 weeks after baseline	Within 3 weeks after Visit 1	Within 2 weeks after Visit 2
MRI safety questionnaire ⁵	X		
Vital signs	X	X	
Concomitant medication review	X	X	
Basal salivary flow		X	
Stimulated salivary flow (including saliva collection)		X	
Schirmer's test (including tear collection)		X	
Plasma metabolomics/proteomics		X	
Urine pregnancy test (FRP)	X ¹	X ¹	
Multi-parametric MRI scan (including contrast)	X		
Meal prior to ¹¹ C-MET PET/CT	X		
Intravenous injection of ¹¹ C-MET PET tracer	X		
¹¹ C-MET PET/CT scan (dynamic and static)	X		
Radio-PK (¹¹ C-MET) sampling (dynamic scan)	X ²		
Measure concentration of ¹¹ C-MET tracer in blood	X ³		
Blood glucose (bedside glucometer)	X ⁴		
Injection of ¹⁸ F-FDG tracer	X ⁴		
¹⁸ F-FDG PET/CT scan	X ⁴		
Measure concentration of ¹⁸ F-FDG in blood	X ^{3,4}		
Salivary gland biopsy		X ⁴	
AE review		X	

AE = adverse event; CT = computed Tomography; FDG = flurodeoxyglucose; FRP = females of reproductive potential; FSH = follicle stimulating hormone; MET = methionine; MRI = magnetic resonance imaging; PET = positron emission tomography; PK = pharmacokinetics;.

1. Females of reproductive potential only
2. Radio-PK sampling (5mL per sample) to be taken at 1, 2, 5, 10, 15, 20, 30 and 40 minutes after injection of ¹¹C-MET PET tracer (number and sampling times are subject to change dependent on emerging data, but no more than 100 mL overall will be taken).
3. To be taken within 5 minutes after the static PET/CT scan (exact time to be recorded).
4. pSS subjects only. If it is not possible to schedule the minor salivary gland biopsy within the 3 week window after Visit 1, this procedure may be performed up to 6 weeks after Visit 1, subject to prior agreement of the medical monitor.
5. The MRI safety questionnaire will not be databased

11.2. Appendix 2: Data Display Standards & Handling Conventions

11.2.1. Study Treatment Display Descriptors

No study treatment is administered in this study. Subject group displays will be described as follows:

Subject Group Descriptions			
Dataset Display		Data Displays for Reporting	
Code	Description	Description	Order [1]
H	Healthy Volunteer	Healthy Volunteer	1
P	pSS Patient	pSS Patient	2

NOTES:

1. Order represents subject groups being presented in TFL, as appropriate.

11.2.2. Baseline Definition & Derivations

11.2.2.1. Baseline Definitions

For all endpoints, baseline will be taken as the value at the screening/baseline except for urine pregnancy test which is taken at baseline 2 (within 4-7 days prior to Visit 1).

11.2.2.2. Derivations and Handling of Missing Baseline Data

No change from baseline calculations are to be conducted. However, if required then the following derivation is to be used:

	Reporting Details
Change from Baseline	= Post-Baseline Visit Value – Baseline Value

NOTES:

- Unless otherwise specified, the baseline definitions specified in Section 11.2.2.1 Baseline Definitions will be used for derivations for endpoints / parameters and indicated on summaries and listings.
- Unless otherwise stated, if baseline data is missing no derivation will be performed and will be set to missing.
- The baseline definition will be footnoted on all change from baseline displays.

11.2.3. Reporting Process & Standards

Reporting Process	
Software	

 • The currently supported versions of SAS software will be used. 	
Reporting Area	
HARP Server	: UK1SALX00175
HARP Area	: /ARPROD/NOCOMPOUND/MID203818/FINAL

Reporting Process	
QC Spreadsheet	: /ARWORK/NOCOMPOUND/MID203818/FINAL/DOCUMENTS
Analysis Datasets	

 Analysis datasets will be created according to Integrated Data Standards Library (IDSL) GSK A&R dataset standards. 	
Generation of RTF Files	

 RTF files will be generated for the final analysis tables and listings only. 	

Reporting Standards	
General	

 The current GSK Integrated Data Standards Library (IDSL) will be applied for reporting, unless otherwise stated: 
 4.03 to 4.23: General Principles 5.01 to 5.08: Principles Related to Data Listings 6.01 to 6.11: Principles Related to Summary Tables 7.01 to 7.13: Principles Related to Graphics 	
Formats	

 All data will be reported according to the actual treatment the subject received unless otherwise stated. GSK IDSL Statistical Principles (5.03 & 6.06.3) for decimal places (DP's) will be adopted for reporting of data based on the raw data collected. Numeric data will be reported at the precision collected on the eCRF. The reported precision from non eCRF sources will follow the IDSL statistical principles but may be adjusted to a clinically interpretable number of DP's. 	
Planned and Actual Time	

 Reporting for tables, figures and formal statistical analyses: 
 For Imaging related outputs, the planned time relative to dosing will be used in figures, summaries, statistical analyses and calculation of any derived parameters, where the output is radio-pharmacokinetic related. For any other outputs the planned time relative to visit 1. The impact of any major deviation from the planned assessment times and/or scheduled visit days on the analyses and interpretation of the results will be assessed as appropriate. Reporting for Data Listings: 
 For Imaging related outputs, planned and actual time relative to study contrast administration will be shown in listings (Refer to IDSL Statistical Principle 5.05.1). For any other outputs, planned and actual time relative to Visit 1 will be shown in listings. Unscheduled or unplanned readings will be presented within the subject's listings. Visits outside the protocol defined time-windows (i.e. recorded as protocol deviations) will be included in listings but omitted from figures, summaries and statistical analyses. 	
Unscheduled Visits	

 Unscheduled visits will not be included in summary tables. Unscheduled visits will not be included in figures. All unscheduled visits will be included in listings. 	

Reporting Standards	
Descriptive Summary Statistics	
Continuous Data	Refer to IDSL Statistical Principle 6.06.1
Categorical Data	N, n, frequency, %
Graphical Displays	

Refer to IDSL Statistical Principals 7.01 to 7.13.	

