## Treatment Arms and Duration

### Subject Participation Flow

Both groups will undergo a Screening/Baseline visit where they will have measurement of basal and stimulated, salivary flow rate (including saliva collection), Schirmer's test and blood samples for biomarkers. The pSS subjects will also have additional clinical scores and patient reported assessments.

Subjects who have completed the screening/baseline will return for an imaging visit (Visit 1). The imaging visit should occur within 6 weeks (42 days) after the screening visit. The following imaging procedures will be performed:

- Group A (healthy volunteers) will undergo an MRI of the salivary glands and C-MET PET/CT (dynamic scan of the salivary glands followed by head to hip static scan).

- Group B (pSS subjects) will undergo an MRI of the salivary glands,  $^{11}\text{C}$ -MET PET/CT (as for Group A) and  $^{18}\text{F}$ -FDG PET/CT (static scan head to hip).

Visit 2 will occur within 3 weeks after Visit 1. Visit 2 will involve measurement of basal and stimulated (chewing paraffin) salivary flow rate (including saliva collection), Schirmer's test (including tear collection), blood samples for biomarkers (metabolomics/proteomics). In addition a minor salivary gland biopsy will be performed on the pSS subjects (Group B). If it is not possible, for logistical or other reasons to schedule the minor salivary gland biopsy within 3 weeks of Visit 1, then this part of Visit 2 may be performed up to 6 weeks after Visit 1, with the prior agreement of the medical monitor.

There will be a Follow up visit within 2 weeks of Visit 2. This may be conducted by telephone for the healthy volunteers (Group A). The pSS subjects (Group B) may have their Follow up visit conducted in person, or by telephone if the Investigator considers it clinically appropriate. Adverse events (AE) will be reviewed at this visit for all of the subjects (Group A and Group B).

Visit 1 and Visit 2 may be split over more than one day.

The total duration of participation in the study will be a maximum of 11 weeks (up to 14 weeks only if it is necessary to delay the minor salivary gland biopsy), although the visits should be completed sooner if feasible.

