## 7.4. Imaging Procedures

### 7.4.1. PET Imaging Procedure

Positron Emission Tomography scans will be acquired on a PET/CT scanner at the imaging centre. The details of the PET imaging procedure, image processing and analysis will be provided by the imaging centre in a PET Imaging Manual.

Subjects will be given a meal before the  $^{11}\text{C}$ -MET tracer injection to stimulate salivary gland function.

Prior to the commencement of the PET scan a venous cannula will be inserted into the subjects arm for administration of  $^{18}\text{F}$ -FDG or  $^{11}\text{C}$ -MET. An additional venous cannula will also be inserted prior to the scan start from which blood samples will be collected at the time points described in the Time and Events tables [Table 2](#) and [Table 3](#). The subject will be positioned in the scanner and sufficient padding will be used to minimize movements during image acquisition. The subject will be monitored continuously by a qualified PET technician.

For  $^{11}\text{C}$ -MET PET scanning, a low-dose CT attenuation scan centred on the salivary glands will be performed for subsequent attenuation and scatter correction of the PET data. Thereafter, the PET scan will commence with an intravenous bolus administration of  $^{11}\text{C}$ -MET (500 MBq) and dynamic scanning of the salivary gland region for approximately 40 minutes. The static scan will follow (within approximately 5 minutes) with the whole body CT followed by the PET covering the head to hip with a duration of same range for approximately 20 to 30 minutes.

For  $^{18}\text{F}$ -FDG PET scanning, scanning will start 60 minutes after intravenous bolus administration of 200 MBq of  $^{18}\text{F}$ -FDG. Blood glucose (bedside glucometer) will be measured before injection of  $^{18}\text{F}$ -FDG tracer. If the glucometer blood glucose is greater than 11.1mmol/l, the  $^{18}\text{F}$ -FDG cannot be injected, and it will be necessary to reschedule

the scan. Advice for Investigators regarding diabetics on oral hypoglycaemic agents will be described in the SRM, and the scan will be scheduled in the morning for these subjects wherever possible. Firstly, a low-dose CT attenuation scan of the area to be scanned (head to hip) will be performed. Thereafter, the PET scan will commence with static scanning acquired for up to 30 to 40 minutes.

After the PET scans, a blood sample will be taken for measurement of radioactivity in blood and plasma (See Section 7.6).

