#### **7.4.2. MRI Imaging Procedure**

As part of the study, eligible subjects will undergo multi-parametric MRI scanning, including administration of a gadolinium based contrast agent at the imaging centre to assess salivary gland inflammation, function and structure in pSS subjects and healthy volunteers. Additionally, the images may be used to identify and delineate the anatomical Regions of Interest (ROI) for individual PET images and to aid in image analysis.

On attendance at the MRI department, subjects will be placed in the scanner and will be prepared for intravenous contrast agent administration. The scanning protocol will include routine localizers, T1 measurement sequences, DCE-MRI acquisition, DW-MRI acquisition, and additional exploratory MRI endpoints, as detailed in the Imaging Acquisition Manual. The total scan time should not exceed 1 hour.

If a scanning failure occurs, if feasible a rescan is allowed within 7 days after the failed scan. There will be a minimum of 24 hours between scans where gadolinium contrast is used.

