7.1.2. Planned Imaging Statistical Analyses

Primary Statistical Analyses
Endpoint(s)

 • ¹¹C-MET PET/CT derived parameters, including but not limited to SUV_{peak}, SUV_{mean}, SUV_{max} • Multiparametric MRI derived parameters, including but not limited to (median and IQR) K_{trans}, (median and IQR) Pure diffusion coefficient (D), (median and IQR) microvascular volume fraction (f) and (median and IQR) ADC.
Model Specification

 • Parameters will be statistically analysed individually using an Analysis of Variance (ANOVA) model. • Terms fitted in the ANOVA model will include: Fixed categorical : Subject group (HV or pSS patient)
Model Checking & Diagnostics

 • Refer to Appendix 9: Model Checking and Diagnostics for Statistical Analyses : Model Checking and Diagnostics for Statistical Analyses.
Model Results Presentation

 • Estimates of Difference (pSS-HV) (or Ratio (pSS/HV) if log_e transformed) and 95% confidence interval for the derived parameters will be presented by ROI¹. • Plots of means (difference or ratio) and 95% confidence interval from the model will be generated for each ROI. • P-values will not be presented as formal hypothesis is not being tested. The interpretation will be based on point estimates and its precision (95% CI).

NOTES :

- [1]: When applicable for a given ROI, the analysis will be separated by the side of the ROI having higher parameter values and lower parameter values, and aggregated over both sides.

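### SAP 11.2.3 would drop an evaluable scan recorded as out of window from imaging summaries and pSS-HV comparisons that do not use the screening-to-scan interval

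*SAP*

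**What the plan says.** **The exclusion rule.** SAP 11.2.3, under planned and actual time: "Visits outside the protocol defined time-windows (i.e. recorded as protocol deviations) will be included in listings but omitted from figures, summaries and statistical analyses". There is no exception for imaging. The same list promises that "The impact of any major deviation from the planned assessment times and/or scheduled visit days" will be assessed for its effect on the analyses, without saying whether the data stay in. Under unscheduled visits it adds: "Unscheduled visits will not be included in summary tables", and treats figures the same way.

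**The window.** Protocol synopsis, Subject Participation Flow: "The imaging visit should occur within 6 weeks (42 days) after the screening visit". Protocol 7.2.1, protocol Table 3 and SAP Appendix 1 give the same 42 days or 6 weeks. None adds a tolerance. The only written extension is for the biopsy at Visit 2.

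**Who is analysed.** SAP 4 and 7.1.1 base the imaging analyses on the Safety population, which is not conditional on timing, unless otherwise specified. Section 11.2.3 then specifies otherwise.

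**What the analyses use.** The only term in the ANOVA of SAP 7.1.2 is "Fixed categorical : Subject group (HV or pSS patient"). The Bayesian analysis in 7.1.3 compares the same endpoints between the same two groups. SAP 11.2.2.2 states: "No change from baseline calculations are to be conducted".

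**Foreseeable delays.** For MRI, protocol 7.4.2 says that "if feasible a rescan is allowed within 7 days after the failed scan". For FDG, protocol 7.4.1 says that above a blood glucose limit the tracer cannot be injected "and it will be necessary to reschedule" the scan. Neither provision refers to the 42 days.

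**The concern.** The rule is tied to a visit window, but the main imaging analyses do not depend on that window. The FDG summaries and the group comparisons use a value measured once, at the scan. A scan made shortly after day 42 measures the same thing as one made shortly before, yet a literal reading leaves it only in a listing.

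The groups hold 4 to 12 subjects, so each scan counts, and 11C-MET PET/CT is capped at 8 healthy volunteers to limit radiation. The study is open-label and imaging results are reviewed while it runs. Whether a late scan counts is therefore better settled by a written analysis rule than by how a deviation is later recorded.

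**Working it through.** **Step 1: reproduce the protocol's precision table.** Protocol 9.2 defines precision as the half-width of a 95% confidence interval for a mean. With h(n) = t(0.975, n−1) × SD / √n and SD = 1:

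- n=4: 3.182/√4 = 1.591 (Table 5: 1.59)
- n=8: 2.365/√8 = 0.836 (Table 5: 0.84)
- n=12: 2.201/√12 = 0.635 (Table 5: 0.64)

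All 12 cells of Table 5 match to two decimals. A normal quantile gives 0.98, 0.69 and 0.57, which do not match, so the table uses t.

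**Step 2: remove one scan from a group mean (SD = 1).**

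| Planned n | Half-width | After loss of one | Change |
|---|---|---|---|
| 12 | 0.635 | 0.672 (n=11) | +6% |
| 8 | 0.836 | 0.925 (n=7) | +11% |
| 4 | 1.591 | 2.484 (n=3) | +56% |

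The last row applies only if healthy-volunteer recruitment stays at its minimum.

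**Step 3: remove one scan from the pSS-HV difference (SD = 1).** The two-group ANOVA interval has half-width t(0.975, n1+n2−2) × SD × √(1/n1 + 1/n2).

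| HV vs pSS | Planned | One HV lost | One pSS lost |
|---|---|---|---|
| 4 vs 8 | 1.36 | 1.53 (+12%) | 1.42 (+4%) |
| 4 vs 12 | 1.24 | 1.39 (+13%) | 1.26 (+2%) |
| 8 vs 8 | 1.07 | 1.12 (+4%) | 1.12 (+4%) |
| 8 vs 12 | 0.96 | 1.00 (+5%) | 0.98 (+2%) |
| 12 vs 12 (MRI) | 0.85 | 0.87 (+2.5%) | 0.87 (+2.5%) |

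**Step 4: use the SDs from the literature table in protocol 9.2.**

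- FDG SUVmax in pSS, SD 0.61: 0.51 to 0.56 at N=8; 0.39 to 0.41 at N=12.
- 11C-MET SUVmax in healthy volunteers, SD 1.5: 1.25 to 1.39 at N=8.
- Ktrans difference, SDs 0.04 (HV) and 0.05 (pSS), pooled, 8 vs 12: 0.0445 to 0.0469 if a healthy volunteer is lost, or 0.0452 if a pSS subject is lost. The literature difference is 0.26 − 0.20 = 0.06.

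**Step 5: how a scan could pass day 42.** An MRI that fails after day 35 can have a rescan seven days later, hence after day 42, within the protocol's own allowance. A rescheduled FDG scan has no stated limit. The documents do not say how either is classed if it falls past day 42. They also give no frequency, so none is assumed.

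**The case against.** The strongest case against is that the rule seldom operates and that the window has a purpose.

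- **Routes around it.** The rule covers only visits recorded as deviations. Protocol 5.3 allows one re-screening, which restarts the window. Protocol 7 allows timing changes by Note to File. The deviation management plan cited in SAP 4.1 was not supplied and may hold a tolerance. All of this stands and narrows the point. None of it is a stated analysis rule, and re-screening does not help a scan already made late.
- **Rescans.** A reader might infer that permitted rescans will be discarded as unscheduled. The documents do not support that. Visit 1 may be split over several days (synopsis; protocol 4.2), so a permitted rescan or rescheduled scan is most naturally part of Visit 1. What remains open is a split that runs past day 42.
- **Screening data matter.** Subject group rests on screening information: ESSDAI and salivary flow for pSS, medical evaluation and laboratory tests for healthy volunteers. Protocol 7.2.1 treats that information as critical for comparing later imaging. This stands as a reason to report the interval and to show results without late scans. It is a weaker reason for automatic removal, because the interval does not enter the model.
- **Which visit is late.** Protocol 7.2.1 words the window backwards from Visit 1, so one could call the screening visit stale instead of the scan late. The synopsis and Table 3 place the limit on the imaging visit.
- **Existing safeguards.** Deviations are reviewed before database freeze, exclusions are documented (SAP 11.4.2), and the effect of major timing deviations is to be assessed. None of these returns the scan to the analysis.

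**Conclusion.** The point holds as a modest improvement to the plan. As written, SAP 11.2.3 omits an evaluable Visit 1 scan recorded as out of window from analyses that do not use the screening-to-scan interval, and neither document states a tolerance.

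The cost is descriptive precision only, since no hypothesis is tested. For one lost scan at SD 1 it is 6% to 11% on a group mean at N=12 or N=8, about 2% to 13% on the pSS-HV difference, and 2% to 5% once both groups have at least 8. These figures assume that one scan is lost and the SD is unchanged.

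Three stronger readings should be resisted. The 56% figure is not typical: it needs recruitment to stop at 4 healthy volunteers and one of those scans to be lost. Nothing shows that results would be biased. Nothing shows that any scan has been or will be lost. For correlations of imaging with screening or Visit 2 measures the window rule is reasonable and is not questioned. Confidence is medium, because the deviation management plan could already settle the matter.

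**What to change.** Amend the bullet in SAP 11.2.3 before database freeze, along these lines:

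> For the imaging summaries and the pSS-HV comparisons, evaluable Visit 1 scans (those with a delivered parameter value), including protocol-permitted rescans and rescheduled scans, are included whatever the screening-to-scan interval, and are flagged in listings with that interval. Where any fall outside the window, the results are also shown without them. For correlations of imaging with screening or Visit 2 measures, the window rule is kept.

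The cost is a few sentences, plus one repeat of the imaging outputs only if a late scan occurs. The display without late scans is what the present rule would report, so nothing now planned is lost.

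The downside is a longer screening-to-scan interval for some subjects, with no outer limit in this wording. That matters because group status and ESSDAI are fixed at screening. The listed interval and the results without late scans would show any effect. The same scan may also count in a comparison but not in a correlation, which a footnote should state.
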